Center for Diabetes Technology

Feasibility of a Decision Support System To Reduce Glucose Variability In Subjects with T1DM

NCT02558491
Version Date: 10-14-2016

A. Purpose/Objectives

The purpose of this study is to demonstrate the safety and feasibility of a decision support system aimed at reducing glucose variability in T1DM patients using continuous subcutaneous insulin infusion (CSII) or multiple daily injections (MDI). The system will be deployed on our portable medical application platform (DiAs) and will include the following elements:

1. An insulin pump or MDI treatment parameters optimization routine, using a month of collected CGM/insulin/meal data
2. An exercise risk warning system, capable of predicting hypoglycemia at the onset of physical activity and advising on mitigating treatments such as insulin adjustment or carbohydrate consumption
3. A smart bolus calculator based on CGM glucose measurements and insulin sensitivity estimation.

Primary Specific Aim:

To demonstrate feasibility and safety of a glucose variability-reducing decision support system, measured by non-inferiority of use of the system compared to standard SMBG-informed CSII or MDI therapy in terms of occurrence of hypoglycemia and percent time spent between 70 and 180 mg/dl as measured by blinded CGM.

Secondary Specific Aims:

To assess the effect size of using the GV advisory system compared to standard CSII or MDI therapy in terms of:

- Occurrence of hypoglycemia during and immediately after exercise
- Glycemic excursion post meals

B. Study Design Overview

Subjects: The study is intended to complete up to 20 subjects with Type 1 Diabetes Mellitus who use continuous subcutaneous insulin infusion (CSII) and up to 20 subjects with Type 1 Diabetes Mellitus who use multiple daily injections (MDI). The study will be a randomized cross-over design with a Control and Experimental admission. The order of the admissions will be randomized. It is estimated that there will be a higher than normal rate of screen failures, dropouts, or withdrawals, thus we intend to set a recruiting target of **70 subjects**.

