As a safety/feasibility investigation, this study is not powered to a specific outcome. Nonetheless, based on prior work and computer simulations we estimate the likely effect size to be large (around 0.7); we therefore have chosen a sample size of 15-20 subjects for each group (CSII and MDI). Using a power analysis with a fixed sample size, significance and 0.8 power, this would allow us to detect an effect size larger than 0.67. In prior studies, 15 subjects have also been considered by regulatory bodies as an appropriate sample size to demonstrate safety in transitional settings for CGM based insulin dosing.

Investigational Site

The University of Virginia has granted the Center for Diabetes Technology the use of a facility designated Research House to perform outpatient studies related to the Artificial Pancreas Project. The facility is located 2.2 miles from the University of Virginia Emergency Department. It is a 4 bedroom/4 bath home with sleeping quarters on the first and second floors. The study team may test up to 3-5 study participants at the same time in the research house.

Minimal Staffing Requirements

At all times, a minimum of one registered nurse, trained in the execution of the protocol as well as in the management of hypo- and hyperglycemia, and a technician, trained in the use and maintenance of the DiAs system will be present during the entire trial. In addition, one of the study physicians and one senior engineer will be on call during the entire admission, with backup MDs and engineers available if the primary contact is unable to be reached. During exercise, there will be a minimum of one nurse per two subjects and one technician per two subjects on site. In the event of five study subjects tested during a single admission, two medically trained personnel will be available during the trial.

D. Study Duration

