The Outpatient Emergency Plan will go into effect should a catastrophic event occur during the study admissions. A catastrophic event is defined as any event that requires emergency treatment by medical professionals that exceed the expected parameters of the protocol. A copy of this plan will be located at the monitoring desk. Staff will be aware of its location at all times.

In the unlikely event of a disruption in 911 phone service, the sites will contact their local non-emergency number (e.g. Charlottesville-UVA-Albemarle Emergency Communications Center can be reached via their non-emergency number [contact]). This number feeds into their main call area where 911 dispatchers are available 24/7.

Event	RN Response	Tech Response
Respiratory Arrest	1) Tell Tech to call 911 2) Begin Basic Life Support	Refer to Study Physician
Cardiac Arrest	1) Tell Tech to call 911 2) Begin Basic Life Support	Refer to Study Physician
Severe Hypoglycemic Event as defined by hypoglycemia accompanied by unconsciousness or seizure	1) Tell Tech to call 911 2) Administer glucagon IM (described in Glycemic Treatment Guidelines Appendix A-6) 3) Remove study pump	Refer to Study Physician
Severe Hyperglycemic Event as defined by β -ketone level ≥ 3.0 mmol/L	1) Discuss correction dose of insulin to administer s.c. via syringe with study M.D. 2) Encourage P.O. water intake 3) Remove study pump and start home insulin pump 4) Go to nearest medical facility for evaluation and treatment.	Refer to Study Physician

Table 3: Outpatient Emergency Plan

ENDPOINTS

We assess the risk to the subject by computing the two classical hypo and hyperglycemia risk indices LBGI and HBGI, based of the blinded CGM data, retrofitted to the SMBG point (see DelFavero et al. JDST 2015). Gaps of less than 3h will be filled using spline based interpolation. LBGI is the primary endpoint.

LBGI and HBGI are measures of glycemic risk that were developed by our groups in the late 1990s and have been shown to be predictive of increased frequency of severe hypoglycemia and increased HbA1c. Detailed formula can be found in Kovatchev et al. Diabetes Care 1998.

In addition we will capture:

- Quality of glycemic control using the percent time spent between 70mg/dl and 180mg/dl.
- Meal insulin coverage will be assessed using Area Under the glucose Curve in the postprandial state.

CLINICAL PROTOCOL

- Glucose variability will be assessed using the Risk Index (sum of LBGI and HBGI).

SUCCESS CRITERIA / GOAL

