As a general rule, a session will be considered useful for data analysis if the subject completes more than 80% of the active study protocol. Subjects completing less than 80% of the protocol may be rescheduled.

Safety and feasibility will mean that using our system, subjects will not increase either their risk of hypoglycemia as measured by LBGI (non-inferiority claim)

STATISTICAL ANALYSIS PLAN

All variables are continuous and though bounded by 0 unlikely to be close to their lower bound, therefore we will compare the control and experimental admissions using a paired Student t-test for equality of mean. Nonetheless, LBGI may be very low in some subjects during the control admission. If such effect is observed in more than 5 subjects, LBGI will be studied using the Wilcoxon signed rank test.

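### The plan claims non-inferiority but tests only for no difference, with no margin or confidence-interval rule for LBGI or percent time 70–180 mg/dl

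*Combined protocol and SAP*

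**What the plan says.** - **Section A, Primary Specific Aim.** Feasibility and safety are to be "measured by non-inferiority of use of the system compared to standard SMBG-informed CSII or MDI therapy", and this is "in terms of occurrence of hypoglycemia and percent time spent between 70 and 180 mg/dl as measured by blinded CGM". The aim names two outcomes.
- **Endpoints.** "LBGI is the primary endpoint". Percent time in range appears only among the additional measures: "Quality of glycemic control using the percent time spent between 70mg/dl and 180mg/dl".
- **Success Criteria / Goal.** Safety and feasibility mean that "subjects will not increase either their risk of hypoglycemia as measured by LBGI (non-inferiority claim"). Percent time is not named.
- **Statistical Analysis Plan.** One paragraph covers all variables: "we will compare the control and experimental admissions using a paired Student t-test for equality of mean". If control-admission LBGI is very low in more than 5 subjects, "LBGI will be studied using the Wilcoxon signed rank test".
- **Section C, sample size.** "As a safety/feasibility investigation, this study is not powered to a specific outcome". The section then gives an expected effect size of around 0.7, 15–20 subjects in each of the CSII and MDI groups, and a detectable effect size of 0.67 at 0.8 power. Alpha and sidedness are not stated, and non-inferiority is not mentioned.

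**The concern.** A non-inferiority claim needs a stated largest acceptable worsening and a rule showing that the data exclude it. The plan has neither. Both planned tests take no difference as the null hypothesis. Rejecting it in the favourable direction shows superiority; rejecting it in the other direction shows harm; not rejecting it shows nothing about how large a harm remains possible.

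The claim at stake is the main one: that the system does not raise the risk of hypoglycemia. Unless LBGI falls significantly, any statement that safety was shown would rest on a rule chosen after the data were seen. The plan does not say that non-significance will be read as safe, but it offers no other link between the test and the claim.

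The outcomes covered by the claim are also unsettled. Percent time 70–180 mg/dl is part of the primary aim, an additional endpoint in Endpoints, and absent from the success sentence.

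**Working it through.** **Inputs.** From Section C: n = 15 to 20 per group, power 0.8, effect size around 0.7, detectable effect 0.67. The analysis paragraph does not say whether CSII and MDI are analysed separately (n = 15 or 20) or pooled (n = 30 or 40), so both are shown. Assumptions, because the documents give no figure: two-sided 5% tests, and differences expressed in SDs of the paired difference (Experimental minus Control).

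**Formula.** For a true standardised difference d, the paired t statistic follows a noncentral t distribution with n − 1 degrees of freedom and noncentrality d√n. Power is the probability that it exceeds the critical value t(0.975, n − 1).

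**1. The plan's own figure.** Solving for 80% power:
- n = 20, two-sided 5%: d = 0.660 (normal approximation (1.960 + 0.842)/√20 = 0.627). Power at 0.67 is 0.811.
- n = 15, one-sided 5%: d = 0.675.
- n = 15, two-sided 5%: d = 0.778.

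So 0.67 is reproduced by a test of a difference, either with 20 subjects two-sided or 15 one-sided. It is not an error, but it is a detectable difference and not a margin.

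**2. How often the planned t-test supports the claim.** Only a significant LBGI fall does so.

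| True LBGI change | n=15 | n=20 | n=30 | n=40 |
|---|---|---|---|---|
| 0 | 0.025 | 0.025 | 0.025 | 0.025 |
| Fall of 0.7 SD | 0.71 | 0.84 | 0.96 | 0.99 |

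The second row applies only if the 0.7 in Section C refers to LBGI, which the section does not say.

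**3. What would pass if non-significance were read as safe.** This is conditional on a reading the plan does not state. Probability of p > 0.05:

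| True LBGI rise | n=15 | n=20 | n=30 | n=40 |
|---|---|---|---|---|
| 0.3 SD | 0.81 | 0.75 | 0.64 | 0.54 |
| 0.5 SD | 0.56 | 0.44 | 0.25 | 0.13 |

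The documents do not say whether rises of this size matter clinically.

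**4. What a proper rule could support.** If non-inferiority requires the upper 95% confidence limit to lie below a margin M, the test is one-sided at 2.5%. With a true difference of 0, its power is the same noncentral t calculation with d = M in SD units.

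| | n=15 | n=20 | n=30 | n=40 |
|---|---|---|---|---|
| Smallest M with 80% power (SD) | 0.78 | 0.66 | 0.53 | 0.45 |

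At M = 0.5 SD the power is 0.44 (n=15), 0.56 (n=20) and 0.87 (n=40). For 80% power, M = 0.5 SD needs 34 pairs and M = 0.3 SD needs 90 pairs in whichever set is analysed. The 95% half-width, t(0.975, n − 1)/√n in observed SDs, is 2.093/√20 = 0.47 at n=20 and 2.145/√15 = 0.55 at n=15.

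**5. Two outcomes.** If both LBGI and percent time had to pass, each with 80% power, joint power would be 0.8 × 0.8 = 0.64 if they were independent, and about 0.73 by simulation at an assumed correlation of 0.8. The plan does not say whether both must pass.

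**The case against.** The strongest reply is that this is a feasibility study, declared as not powered for any outcome, and that the sponsor expects a large benefit. If LBGI truly falls by 0.7 SD, the planned test gives a significant fall with probability 0.84 at n=20, and that would establish non-inferiority. The figure of 0.025 and the required numbers of pairs all assume a true difference of exactly 0. A true benefit reduces what is needed: with a 0.5 SD margin and a 0.2 SD benefit the effective distance is 0.5 + 0.2 = 0.7 SD, and power at n=20 is again 0.84. The t-test figures also do not apply exactly if LBGI goes to the Wilcoxon test.

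These are fair limits on the illustrations, and the sizes above should be read as conditional. They do not supply the missing rule. Lack of formal powering excuses low power; it does not excuse a non-inferiority claim without a margin. A confidence interval reported alongside the t-test does not help either, because no pre-set value exists to compare it with.

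The word *either* in the success sentence, with no second item after it, suggests that an outcome was lost in drafting or in extraction from the PDF. The omission of percent time there is therefore less certain than the discrepancy between the primary aim and Endpoints, which stands.

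Appendices A-3, A-6 and A-10 are not in the supplied text, but they are cited for optimisation limits, glycemic treatment and a monitoring form, and nothing refers to them for statistics.

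**Conclusion.** The concern holds. The primary aim and the success criterion claim non-inferiority, the only planned analyses are tests of no difference, and no margin or interval rule exists for either outcome. This is a mismatch between claim and analysis, not just missing detail, and it must be corrected before the data are analysed.

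That conclusion needs no numerical assumption. Its size does: at a two-sided 5% level and in SDs of the paired difference, the planned t-test supports the claim with probability 0.025 when the two admissions truly give equal LBGI, rising to 0.71–0.84 per group (n = 15–20) only if a true fall of 0.7 SD is present. Under true equality, a group of 15–20 can support a margin no smaller than 0.78–0.66 SD with 80% power. Whether margins that wide are clinically acceptable cannot be judged from the documents, which give no SD and no threshold for LBGI.

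**What to change.** Choose one of two routes before analysis.

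**Keep the claim.**
1. For LBGI, replace the equality rule with: *Non-inferiority is concluded only if the upper limit of the two-sided 95% confidence interval for Experimental minus Control is below M*, with M fixed and justified in LBGI units. If the Wilcoxon route is taken, apply the same rule to the matching Hodges–Lehmann interval.
2. For percent time 70–180 mg/dl, state the mirror-image rule (lower 95% limit above minus a pre-set margin) and whether both outcomes must pass, or remove it from the non-inferiority aim. Make the aim, Endpoints and Success Criteria agree.
3. State whether the rule applies to CSII and MDI separately or pooled.

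**Drop the claim.** If no margin can be justified, or the justified margin is smaller than the sample supports, delete the non-inferiority wording from the Primary Specific Aim and Success Criteria. Report paired estimates with 95% confidence intervals without declaring safety shown. This fits Section C.

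On either route, Section C should state the alpha, sidedness and n behind 0.67 and say that it is a detectable difference.

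**Cost.** Wording only if the claim is deleted. Planning for 80% power with no true difference, it is also wording only if the justified margin is at least about 0.78 SD (15 per group), 0.66 SD (20 per group) or 0.45 SD (40 pooled). A 0.5 SD margin needs 34 pairs, which the pooled 40 would cover but a single group would not; 0.3 SD needs 90. The price is a weaker safety statement than the plan now makes.

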Subjects will use their own insulin parameters, including basal rate or basal insulin dose insulin sensitivity factor and carbohydrate ratio, and determine their own insulin usage during the Control admission.

MDI subjects will be provided with an insulin pen (NovoPen Junior, NovoPen Echo, or Companion Medical inPen Smart Pen) with short-acting insulin for treatment during the Experimental admission. These pens are capable of delivering insulin in 0.5 unit increments and are FDA approved but for the Smart Pen which is under 510(k) review (see letter of Authorization). If this option is selected, the Companion Medical pen, known as the InPen, will be used in the trial. This insulin pen contains computer chip technology built into the base and

has Bluetooth LE wireless capability. It will collect the subject's data and then transmits it to an app that contains a dose calculator and also calculates real-time insulin on board (IOB). The insulin pen has remote monitoring, permitting the subject to inform the study team of their insulin dose, BG and carbohydrates. An inPen User Guide will be available to all MDI subjects if this smart pen is used in the trial. If this pen is not available at the time of the trial, a pen that can deliver in 0.5 unit increments will be used, such as the Lilly Luxura insulin pen.

The study is also designed to test the capacity of our exercise advisory system to avoid or limit exercise-induced hypoglycemia, by challenging the subject with two 3x15min exercise bouts.

Study Diagram

Visit 1: Screening Visit. All subjects will be consented and receive a history and physical. Study eligibility will be reviewed. After a subject completes the screening criteria, the subject will be randomized to the Experimental or Control admission first.

Visit 2: CGM Placement & Training. All subjects will receive training on the use of the continuous glucose monitor (CGM) and study glucometer prior to the Experimental admission. Approximately 28 days of **blinded** CGM data will be collected with a total of 14 valid days needed to participate in the research house/hotel admission. Visit 1 and 2 can be done on the same day.

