Visit 3: Data Collection Period. Blinded CGM data will be collected prior to the Experimental admission and analyzed by the study team to determine the optimal insulin therapy parameters that will be used during the Experimental admission. For CSII users, the insulin pump and CGM downloads will be reviewed approximately 72 hours before the Experimental admission by the study team to ensure proper collection procedures. For MDI users, data entered into the MySugr app and CGM downloads will be similarly reviewed. Subjects will also wear a 'Fitbit' to collect information activity, exercise, heart rate, and sleep. An anonymous Gmail account will be established for each subject. An app will be placed on the subject's smartphone or subject's personal laptop to facilitate weekly downloading of the Fitbit data. Additional Data Collection Periods may be requested to ensure proper data collection.

Visit 4 and 5: Research House/Hotel Admission. The Experimental and Control admission will be separated by approximately 4 weeks, 8 weeks or 12 weeks. The order of these two visits will be randomly selected. Subjects will be admitted to the research house/hotel at ~16:00-17:00 and will be discharged after approximately 48 hours.

Figure 1: Study Design

C. Sample Size and Investigational Sites

This study will be conducted at the University of Virginia Center for Diabetes Technology (CDT). Twenty subjects (N=20) with Type 1 Diabetes Mellitus who use CSII and twenty subjects (N=20) with Type 1 Diabetes Mellitus who use MDI to treat their diabetes will be needed to complete the protocol. The studies will be conducted at the CDT Research House as noted below. The study may also occur at a local hotel. Vulnerable populations (i.e. pregnant women, prisoners, etc.) will be excluded from participation. Based on our experience with similar studies, we estimate an higher than normal screen failures, dropouts, or withdrawals due to the data collection requirements and admission time restrictions; thus we intend to set a recruiting target of 70 subjects.

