The duration of the study for each patient is intended to be up to 10 weeks. Subjects will be permitted up to a two month delay if unable to attend their second research house/hotel visit as initially scheduled. However, if more than 100 days elapse between the Control and Experimental admissions, the subject will be discontinued and replaced by another subject. Admissions to the research house may be repeated if the admission or the data collection is suspended or inadequate. Screening or re-screening labs can be done either at the UVA CRU or at a LabCorp that is convenient to the subject. Lab values collected from a prior medical appointment may be used if dated within 4 weeks of the screening appointment.

E. Inclusion and Exclusion Criteria

Inclusion Criteria: To be eligible for the study, a subject must meet the following criteria:

1. Clinical diagnosis based on investigator assessment, of type 1 diabetes for at least one year and either using insulin pump therapy for at least 6 months or MDI therapy for at least 6 months; 1-2 basal insulin injections per day, consistent in amount and timing (administering at approximately the same time each day). The following MDI therapy will be permitted:

CLINICAL PROTOCOL

- Subjects using Glargine (100 U/mL) once or twice daily.
- Subjects using Detemir (100 U/mL) twice daily.
- Subjects using Degludec (100 U/mL) once daily

A. Historical criteria for documented hyperglycemia (at least 1 must be met):

- i. Fasting glucose ≥ 126 mg/dL.
- ii. Two-hour OGTT glucose ≥ 200 mg/dL.
- iii. Hemoglobin A1c $\geq 6.5\%$ documented.
- iv. Random glucose ≥ 200 mg/dL with symptoms.
- v. No data at diagnosis is available but the participant has a convincing history of hyperglycemia consistent with diabetes.

B. Historical criteria for requiring insulin at diagnosis (1 must be met):

- i. Participant required insulin at diagnosis and continually thereafter.
- ii. Participant did not start insulin at diagnosis but upon investigator review likely needed insulin (significant hyperglycemia that did not respond to oral agents) and did require insulin eventually and used continually.
- iii. Participant did not start insulin at diagnosis but continued to be hyperglycemic, had positive islet cell antibodies – consistent with latent autoimmune diabetes in adults (LADA) and did require insulin eventually and used continually.

2. Age 15– 65 years old.

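### Low-priority, cheap improvement: the randomised cross-over is tested on LBGI with no period term, so the result depends on the completers' sequence split if there is a period effect

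*Combined protocol and SAP*

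**What the plan says.** Section B (Study Design Overview) describes a two-admission cross-over: "The order of the admissions will be randomized". The Study Diagram places the allocation at Visit 1, where "the subject will be randomized to the Experimental or Control admission first". No allocation ratio, blocking or stratification is given.

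The Statistical Analysis Plan compares the admissions "using a paired Student t-test for equality of mean". If LBGI is very low at the Control admission in more than 5 subjects, "LBGI will be studied using the Wilcoxon signed rank test". Neither test uses the order of the admissions, and no period or sequence term appears elsewhere.

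LBGI is the primary endpoint (Endpoints). Under Success Criteria / Goal the claim is that "subjects will not increase either their risk of hypoglycemia as measured by LBGI (non-inferiority claim".

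Section C plans 15 to 20 subjects per treatment group (CSII, MDI) and expects an unusually high rate of screen failures, "dropouts, or withdrawals due to the data collection requirements and admission time restrictions". Section D says that when too long passes between admissions "the subject will be discontinued and replaced by another subject". The individual stopping criteria also allow replacement of non-completers. Nothing says that a replacement takes the sequence of the subject replaced.

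**The concern.** In a two-period cross-over, anything that differs systematically between the first and second admission enters the Experimental-minus-Control difference with opposite signs in the two sequences. It cancels from the mean only if the sequences are equally represented. A paired test that ignores order also leaves it in the error term.

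Equal representation among completers is not secured here. Subjects are randomised before the data collection and admissions that are expected to cause dropout, replacements carry no sequence rule, and at n=15 an equal split is impossible. Because the claim is non-inferiority on LBGI, the direction of a shift matters: one that lowers the difference makes the safety claim easier to reach, and one that raises it makes the claim harder. The trial will see only one split, and the planned test cannot separate treatment from period in it.

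**Working it through.** **Inputs.** From the documents: n = 15 to 20 per group, power 0.8, detectable effect 0.67 (section C). Assumed, because the documents do not state them: two-sided 5% level; a one-sided 2.5% confidence-limit rule for non-inferiority (no margin, level or rule is given); normal paired differences with SD 1; period effect p from 0 to 0.5 SD; simple randomisation where averages are taken.

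**The plan's own figure.** A paired t-test with n=20 at two-sided 5% has 80% power at an effect of 0.660 and power 0.811 at 0.67. The stated figure reproduces at n=20. At n=15 the detectable effect is 0.778.

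**Model.** Let tau be the treatment effect and p the second-minus-first-admission effect. Let n_CE be the number of Control-first and n_EC the number of Experimental-first completers. Experimental minus Control has mean tau + p in Control-first subjects and tau − p in Experimental-first subjects. Then:

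- Paired estimate: mean tau + p(n_CE − n_EC)/n, true sampling SD 1/√n. The period effect does not change that SD at a fixed split.
- Variance that the paired test estimates: 1 + p² × n/(n−1) × (1 − ((n_CE − n_EC)/n)²). It exceeds 1 whenever p ≠ 0 and both sequences are present.
- Period-adjusted estimate (average of the two sequence-specific means): mean tau, SE ½√(1/n_CE + 1/n_EC), n−2 df.

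Example, 10:10 and p=0.5: variance 1 + 0.25 × 20/19 = 1.263, so the estimated SE is √(1.263/20) = 0.251 against a true 0.224 (ratio 1.12). At 12:8 and p=0.5 the shift is 0.5 × 4/20 = 0.10, with estimated SE 0.250 against 0.228 adjusted.

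**Fixed splits, n=20, paired test, at p = 0.1, 0.3, 0.5**

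| Split | Size of shift | Two-sided type I | One-sided false non-inferiority |
|---|---|---|---|
| 10:10 | 0, 0, 0 | 4.9%, 4.1%, 2.9% | not tabulated; no shift |
| 12:8 | 0.02, 0.06, 0.10 | 5.0%, 4.8%, 4.5% | 3.0%, 3.7%, 4.0% if the shift lowers the difference; 2.0%, 1.1%, 0.5% if it raises it |
| 14:6 | 0.04, 0.12, 0.20 | 5.2%, 7.0%, 9.7% | not tabulated |

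The adjusted test holds 5% two-sided and 2.5% one-sided throughout. (Simulation runs of the 14:6 row vary by about 0.1 point.) At 10:10, paired power for 0.67 is 0.81, 0.78 and 0.74, against 0.81 adjusted.

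**How likely is an uneven split?** With 20 completers under simple randomisation, 12:8 or worse has probability 50% and 14:6 or worse 11.5%. If 26, 30 or 34 per group are allocated equally and dropout is unrelated to sequence (assumed), 12:8 or worse has probability 16%, 25% or 30%, and 14:6 or worse at most 1.3%.

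**Averaged over simple randomisation.** False non-inferiority is 2.5% for both tests at every p. Average power for 0.67:

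| p | n=20 paired | n=20 adjusted | n=15 paired | n=15 adjusted |
|---|---|---|---|---|
| 0 | 0.81 | 0.79 | 0.68 | 0.64 |
| 0.1 | 0.81 | 0.79 | 0.67 | 0.64 |
| 0.2 | 0.80 | 0.79 | 0.66 | 0.64 |
| 0.3 | 0.78 | 0.79 | 0.64 | 0.64 |
| 0.5 | 0.72 | 0.79 | 0.58 | 0.64 |

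The curves cross near p = 0.25 (n=20) and p = 0.3 (n=15).

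**The case against.** The strongest reply is that nothing is broken. The paired test respects the pairing and has correct size over the randomisation, and section C says the study is not powered to a specific outcome. The documents give neither a size nor a mechanism for a period effect. Blinded CGM, supervised dosing and replicated meals during the admissions argue for a small one, and at p = 0.1 the gain is negligible to small. Below about 0.25 to 0.3 SD, adjustment loses average power. The largest error rate above needs a 14:6 split together with the top of the assumed range. The absence of a non-inferiority margin is a larger gap.

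All of that stands, and it sets the priority. It does not remove the conditional argument: the result will be read at the one split that occurs, and adjustment makes it correct there.

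A reader might go further and infer that the planned test is invalid, or that its two-sided error is inflated at any uneven split. The figures do not support this: the average size is nominal, and at 12:8 the two-sided rate does not exceed 5%. A reader might also infer that a period effect is likely because data collection precedes the Control admission only in Experimental-first subjects. That asymmetry is not evidence of a period effect.

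**Conclusion.** The point holds as a low-priority improvement, not as an error. If there is a period effect, the planned test gives an LBGI difference that is shifted when the completers' split is uneven, and an estimated standard error that is too large whenever both sequences are present. The true sampling SD at a given split is unchanged, so at 10:10 the paired test is conservative rather than wrong.

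For p up to 0.5 SD at n=20 the consequence runs from negligible to 7 points of power at 10:10, or to a one-sided rate between 0.5% and 4.0% instead of 2.5% at 12:8. The algebra is certain. The practical size is not, because p, the one-sided rule and the randomisation scheme are all assumed. The signed rank fallback has the same gap.

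**What to change.** Analyse LBGI with treatment and period as fixed effects and subject as random. For complete pairs this is the average of the two sequence-specific mean differences, with pooled within-sequence SD and n−2 df. State the randomisation scheme, and report the sequence split among analysed subjects. Admissions may be repeated or rescheduled, so add a rule that such a session belongs to the period of the admission it replaces.

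If the rank fallback is triggered, keep the signed rank test. As a sensitivity analysis, add a rank-sum comparison of period differences (first minus second admission) between the sequences. The sequences then differ by twice the treatment effect, so halve the estimate or double any margin. It should not replace the signed rank test, because its power cost near the LBGI floor can be judged only from assumed distributions.

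**Cost.** SAP wording and the period rule; no new data. With no period effect at n=20, power for 0.67 goes from 0.811 to 0.809 at 10:10 (under 1 point), 0.793 at 12:8 (about 2) and 0.738 at 14:6 (about 7). On average the loss is about 2 points at n=20 and 3 to 4 at n=15.

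**Limits.** A period term does not remove carry-over. Nor does it remove an effect d of data collection that falls between the admissions only in Control-first subjects: this adds d/2 to the adjusted estimate and d × n_CE/n to the paired one.
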